9.3 POPULATIONS FOR ANALYSES

The analysis dataset will be modified intention to treat (ITT), which will include all participants who received study drug and who have 3-month outcome data for EEsAI and endoscopy. We will have a secondary analysis dataset for a sensitivity analysis where the last available EEsAI value will be carried forward for any participants who terminate the study or are lost to follow-up.

The safety analysis dataset will be all participants who received study drug, regardless of follow-up time or other outcomes.

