1 PROTOCOL SUMMARY

1.1 SYNOPSIS

Title: A multi-center, randomized, double blind, parallel-arm, placebo controlled trial of mepolizumab for treatment of adults and adolescents with active eosinophilic esophagitis and dysphagia-predominant symptoms

Study Description: This multi-center, randomized, double blind, parallel-arm, placebo controlled trial will determine whether mepolizumab is more effective than placebo for improving symptoms of dysphagia and decreasing esophageal eosinophil counts in adults and adolescents with active eosinophilic esophagitis after an initial 3-month treatment course and will also assess the impact of an additional 3-months of treatment.

Objectives: Primary Objectives:

1. To determine whether mepolizumab is more effective than placebo for improving symptoms of dysphagia as measured by the validated Eosinophilic Esophagitis Symptom Activity Index (EEsAI) in adults and adolescents with active eosinophilic esophagitis after a 3-month treatment course.
2. To determine whether mepolizumab is more effective than placebo for decreasing esophageal eosinophil counts in adults and adolescents with active eosinophilic esophagitis after a 3-month treatment course.

Secondary Objectives:

1. To determine predictors of symptomatic and histologic response to mepolizumab treatment, including potential biomarkers.
2. To assess durability of symptomatic and histologic response to mepolizumab after 6 months of treatment in patients initially randomized to the active medication (this includes a 3-month blinded second phase of treatment).
3. To assess histologic response to a lower dose of mepolizumab treatment in patients initially randomized to the placebo arm (this will be in a 3-month blinded second phase); symptom response will also be assessed in this phase.
4. To assess safety of mepolizumab over 3 and 6 months of treatment (this includes both 3-month study phases).

Outcomes:

Primary Outcome:

1. Mean change in dysphagia as measured by the EEsAI score (7-day recall) from baseline to 3-months post-treatment.

Secondary Outcomes:

1. Proportion of patients who have clinical remission as defined by an EEsAI score of ≤ 20 .
2. Proportion of patients who have a clinical response, as defined by an EEsAI score decrease of ≥ 20 points.
3. Absolute peak eosinophil count (measured in eos/hpf) after 3-months of treatment.
4. Levels of histologic response after 3-months of treatment including < 15 , ≤ 6 , and ≤ 1 eos/hpf.

[figure not shown]

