6.5.1 PROHIBITED TREATMENTS

No dietary changes, dilations, changes in baseline PPI medication dose, changes in inhaled or intranasal steroid doses, or administration or oral, topical/swallowed, or systemic steroids will be allowed during the study period (from consent through the end of treatment period). Esophageal dilation at the screening or month 3 endoscopy will result in study exit. However, dilation may be performed during or after the month 6 endoscopy, if clinically indicated.

If a subject has severe persistent or recurrent symptoms, or experiences a food impaction during the treatment period, rescue medications and procedures to treat EoE are allowed for clinical purposes. The sponsor will not supply rescue medications, and these would need to be prescribed as clinically indicated by the subject's physician. However, if such medications or treatments are required, the participant would be considered a treatment failure and would exit the study. If this happens, and at the discretion of the site-Investigator or sponsor-investigator it is safe and feasible to do so, the subject should return for an early termination visit.

Although the use of rescue medications is allowable at any time during the study, if safe and feasible to do so the use of rescue medications should be delayed until either the 3-month or 6-month assessments are completed. Rescue medications or treatments administered after the month 6 EGD will not result in study exit. The date and time of rescue medication administration as well as the name and dosage regimen of the rescue medication must be recorded.

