7 STUDY INTERVENTION DISCONTINUATION AND PARTICIPANT DISCONTINUATION/WITHDRAWAL

7.1 DISCONTINUATION OF STUDY INTERVENTION

Subjects may choose to withdraw from participation in the study at any time upon their request without penalty. Additionally, the investigator and sponsor may withdraw a subject from the study in the event of an intercurrent illness, adverse event (AE), treatment failure, protocol violation, cure, and for administrative or other reasons. Discontinuation from study treatment does NOT automatically lead to a complete withdrawal from the study. Subjects discontinuing from study treatment are strongly encouraged to complete early termination procedures and safety follow up.

Investigators should withdraw study treatment from subjects if any of the following occur:

- Pregnancy
- Lost to follow up
- Hypersensitivity / systemic allergic reaction to the study treatment requiring administration of epinephrine
- The subject meets an exclusion criterion (either newly developed or not previously recognized) that precludes further study participation

- Worsening symptoms or disease progression that, in the opinion of the investigator, requires either esophageal dilation or EoE treatment with either topical or systemic steroids during the treatment period
- Any adverse event that, in the opinion of the investigator, precludes safe continuation with the study protocol and study dosing
- Significant study intervention non-compliance, in the opinion of the investigator
- Any condition that, in the judgment of the site-PI or Sponsor, would compromise the ability of the patient to comply with the study protocol or complete the study

Before deciding to discontinue study treatment, the site-PIs should consult the Sponsor-Investigator and study medical monitor, regardless of the reason for discontinuation. Subjects who withdraw and have received at least 1 dose of study drug should return to complete the early termination visit.

The reason for participant discontinuation or withdrawal from the study will be recorded on the eCRF. Subjects who sign the informed consent form and are randomized but do not receive the study intervention may be replaced. Subjects who sign the informed consent form, and are randomized and receive the study intervention, and subsequently withdraw, or are withdrawn or discontinued from the study, will also be replaced such that the goal enrollment at the end of the study can be achieved.

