7.2 LOST TO FOLLOW-UP

A participant will be considered lost to follow-up if he or she fails to return for a scheduled study visit and is unable to be contacted by the study site staff.

The following actions must be taken if a participant fails to return to the clinic for a required study visit:

- The site will attempt to contact the participant and reschedule the missed visit at the earliest possible time and counsel the participant on the importance of maintaining the assigned visit schedule and ascertain if the participant wishes to and/or should continue in the study.
- Before a participant is deemed lost to follow-up, the site-investigator or designee will make every effort to regain contact with the participant (where possible, 3 telephone calls and/or email contacts, if necessary, a certified letter to the participant's last known mailing address or local equivalent methods). These contact attempts should be documented in the participant's medical record or study file.
- Should the participant continue to be unreachable, he or she will be considered to have withdrawn from the study with a primary reason of lost to follow-up.

To assist with retention, study staff may contact subjects via email if the participant provided an email address at the time of consent. The email will not contain identifying or health related information, rather will request that the participant get in contact with us to complete required study procedures. Subjects may also receive emails directly from the data management system (REDCap) with links to their secure survey.

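### The primary efficacy set requires both month-3 EEsAI and month-3 endoscopy, so the symptom comparison drops some dosed patients, and no primary rule covers patients rescued before month 3

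*Combined protocol and SAP*

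**What the plan says.** Section 9.3 names the set for the main efficacy analysis, "which will include all participants who received study drug and who have 3-month outcome data for EEsAI and endoscopy". Its next sentence adds a secondary dataset, for sensitivity only, in which the latest EEsAI is carried forward for people who stop early or are lost. Section 9.4.1 excludes those without outcome data from the primary analyses and says that reasons for missing data will be recorded. It adds a check in which people lost to follow-up are set first to failure and then to success.

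The primary outcome in 1.1 is "Mean change in dysphagia as measured by the EEsAI score (7-day recall) from baseline to 3-months post-treatment". Section 9.4.2 compares it by analysis of covariance on baseline EEsAI and notes that the score is collected monthly.

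If rescue is needed, 6.5.1 says that "the participant would be considered a treatment failure and would exit the study" and that, where safe and feasible, "the subject should return for an early termination visit". It also asks that "if safe and feasible to do so the use of rescue medications should be delayed until either the 3-month or 6-month assessments are completed", and lists among the items to record: "The date and time of rescue medication administration". Under 7.1, dosed participants who withdraw or are withdrawn "will also be replaced such that the goal enrollment at the end of the study can be achieved". Section 7.2 treats a participant as "lost to follow-up if he or she fails to return for a scheduled study visit and is unable to be contacted".

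**The concern.** Membership of the primary set depends on events after randomisation: reaching month 3, completing the questionnaire and having the endoscopy. The endoscopy condition suits the histologic and EREFS outcomes, but a symptom score can be analysed without it.

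Rescue raises a second problem. Section 6.5.1 classifies a rescued patient as a treatment failure, but nothing in section 9 uses that classification. Without month-3 data, such a patient leaves the primary comparison and a new patient is enrolled. That restores the count, not the lost outcome. The remission and response definitions in 9.4.3 do not mention rescue either.

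At stake is what the primary estimate describes: patients who reached month 3 with both assessments, or all dosed patients in their randomised arm.

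**Working it through.** **1. Who falls where, reading the sections together**

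- *Month-3 EEsAI, no endoscopy, still in the study.* Outside the primary set. Not clearly in the carried-forward set, which covers those who terminate or are lost.
- *Rescued before month 3, no month-3 data.* Outside the primary set. In the carried-forward set, but the value carried may come from the early termination visit, which includes an EEsAI (8.4, Visit Months 3, 6 and Early Termination) and can follow rescue. Section 2.1 itself notes that dilation can improve symptoms while eosinophilia persists, so a failure could be carried forward as improved.
- *Rescued, returns for early termination.* Outside the failure/success check if 9.4.1 is read with the 7.2 definition, because this person came back.
- *Early-termination EEsAI and endoscopy.* The plan does not say whether they count as month-3 data.

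**2. The plan's own sample size (9.2)**

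Inputs: mean decreases 15 and 32 (difference 17), SD 20, two-sided alpha 0.05, power 0.9.

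n = 2 × (1.960 + 1.282)² × 20² / 17² = 29.1, rounded up to 30 per group. The stated figure reproduces.

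**3. Cost of the endoscopy condition alone**

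Two-sample t power, SD 20. The number lost is an assumption.

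| Analysed per arm | Power, 17 points | Power, 20 points |
|---|---|---|
| 30 | 0.899 | 0.968 |
| 29 | 0.889 | 0.963 |
| 28 | 0.878 | 0.957 |
| 27 | 0.865 | 0.950 |

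**4. Effect of leaving out early exits**

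Assumptions: 36 dosed per arm, x exits, each exit scored as zero change. The documents do not say whether 15 and 32 describe completers or all dosed patients, so both readings are shown.

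- Reading A, 15 and 32 are completer means: all-dosed mean = mean × (36 − x)/36.
- Reading B, 15 and 32 are all-dosed means: completer mean = mean × 36/(36 − x).

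With 6 exits per arm:
- A: 32 × 30/36 − 15 × 30/36 = 26.67 − 12.50 = 14.2
- B: 32 × 36/30 − 15 × 36/30 = 38.4 − 18.0 = 20.4

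| Exits placebo/mepolizumab | A: all-dosed difference when completers show 17 | B: completer difference when all dosed show 17 |
|---|---|---|
| 6/6 | 14.2 | 20.4 |
| 6/2 | 17.7 | 15.9 |
| 2/6 | 12.5 | 22.5 |

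In rows 6/6 and 2/6 the completer figure is larger than the all-dosed figure. In row 6/2 it is smaller. The sign depends on the unknown exit pattern.

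Replacement does not undo this. With 36 completers plus 6 exits per arm (an assumed reading of the enrolment goal), reading A gives (32 − 15) × 36/42 = 14.6.

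**5. Binary clinical response (decrease of at least 20 points)**

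Normal approximation, reading A, SD 20:
- Completers: P(N(15, 20) ≥ 20) = 0.401 and P(N(32, 20) ≥ 20) = 0.726, a difference of 32 percentage points.
- With 6 rescued per arm counted as non-responders: 0.401 × 30/36 = 0.334 and 0.726 × 30/36 = 0.605, a difference of 27 points.

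**The case against.** Four arguments have weight.

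- EEsAI and endoscopy belong to the same month-3 visit, so few patients should have one without the other, and step 3 shows little power lost. This stands.
- The plan asks for rescue to be delayed to the assessment where possible and provides an early termination visit. Both should reduce the number affected, but neither says how the remaining patients are analysed.
- The failure/success check is introduced as a check for missing data in general, so a wider reading than 7.2 is plausible. That is a reason to write the wider scope down.
- Analysis of covariance at month 3, adjusted for baseline, is an accepted primary method. This stands too.

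A reader might infer more than the text supports. It would be wrong to say that the plan has no other efficacy set: 9.3 defines the carried-forward dataset, which brings back exits and can use months 1 and 2. It would be wrong to say that the primary analysis is biased in favour of mepolizumab: step 4 gives both signs. It would also go too far to say that a repeated-measures model must replace the primary analysis. Fitted to pre-rescue scores, that model estimates the contrast as if rescue had not been given, so it does not count rescued patients as failures either.

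**Conclusion.** The point holds for the primary comparison and should be fixed. The set is conditioned on post-randomisation completion, its endoscopy condition is unnecessary for a questionnaire outcome, and the treatment-failure label in 6.5.1 has no counterpart in section 9. The existing sensitivity analyses only partly cover this.

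The size cannot be stated, because the documents give no rescue or exit rate. The figures in steps 4 and 5 rest on assumed exit counts and zero change in those who exit. They show that several points either way are possible, not what will happen. The consequence is an estimate whose population is unclear and an open choice over early-termination data. The sample size calculation is not in error on this account.

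**What to change.** - **9.3, EEsAI outcomes:** delete the endoscopy condition. Keep it for histologic and EREFS outcomes.
- **9.3, early-termination data:** state that a post-rescue score is not month-3 data, and say whether a pre-rescue one is.
- **9.3, carried-forward set:** carry only EEsAI obtained before rescue.
- **9.4.3, remission and response:** count patients rescued before month 3 as non-responders, in line with 6.5.1. Keep replaced patients in these analyses in their randomised arm.
- **9.4.1, failure/success check:** extend it to everyone who exits before month 3, with rescued patients kept as failures in both runs.
- **9.4.2:** keep the baseline-adjusted analysis of covariance as primary, on the corrected set. A repeated-measures model on the EEsAI already collected at months 1 to 3 may be added as a sensitivity analysis, with its as-if-no-rescue reading stated.

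Rescued patients without a month-3 score would still be absent from the primary covariance analysis. The binary outcomes and sensitivity analyses would then account for them explicitly.

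The cost is rewording and a little more analysis. No visit or questionnaire is added. Rescue medication dates are already required. Dates of rescue procedures are also needed, which may mean one more case report form field (the form is not among the documents). The estimated effect may be smaller, as in step 5: a response difference of 27 instead of 32 percentage points under the assumed 6 rescued per arm.

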9.4 STATISTICAL ANALYSES

9.4.1 GENERAL APPROACH

Descriptive statistics will be used to describe the data. Categorical variables will be presented as proportions and means will be presented with standard deviation and range. If the data are not normally distributed, medians and interquartile ranges will be presented rather than means, and non-parametric testing will be used. For inferential tests, a p value < 0.05 will be considered significant and all tests will be two tailed. All statistical estimates (e.g., medians, proportions, incidence rates, mean differences, correlations, etc.) will be tabulated along with corresponding confidence intervals (CIs).

Interpretation of CIs will play a major role as an integral part of the analysis of the data in concert with any statistical hypothesis tests. To avoid over-reliance on p-values, the magnitudes of estimates and the corresponding confidence intervals will be a focus of the analyses. Reasons for missing data will be investigated and recorded for purposes of statistical analyses. Because of the study design and outcome assessment, primary analyses will require exclusion of participants without outcome data. However, we will perform sensitivity analyses for missing data, initially assigning participants lost to follow up to treatment failure, then assigning them to treatment success and comparing the results, a technique that has been successful in prior clinical trials conducted by our group. For all outcomes, the null hypothesis is that there is no difference between the study groups. All hypothesis tests that are observed to be NOT statistically significant will be reported as being inconclusive.

The study statistician on this study will be [name].

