9.2 SAMPLE SIZE DETERMINATION

The study is powered for the primary outcome, the EEsAI score, which can range from 0-100, with a score of ≤ 20 indicating clinical remission, and a decrease of ≥ 20 points indicating a meaningful clinical response. Based on this, we estimate that with a sample size of 30 patients in each group we would be able to detect a difference in the mean change in EEsAI score of as little of 17, with a power of 0.9 at an α of 0.05, which would allow us to detect the clinically meaningful difference of 20 (see Table). Assuming a 20% dropout rate, we plan to randomize 36 patients in each group.

Table: Sample size considerations

Estimated mean decrease in EEsAI score after 12 weeks of treatment*				
Placebo	Mepolizumab	α	Power	N per group
10	30	0.05	0.9	22
15	30	0.05	0.9	38
20	30	0.05	0.9	85
10	35	0.05	0.9	14
15	35	0.05	0.9	22
15	32	0.05	0.9	30
20	35	0.05	0.9	38
10	40	0.05	0.9	10
15	40	0.05	0.9	14
20	40	0.05	0.9	22

*SD 20 for all

For the secondary outcome of proportion of patients with an EEsAI score ≤ 20 indicating clinical remission, a sample size of 30 in each group would allow us to detect as little as a 40% difference in remission rates between placebo and active therapy with a power of 0.9, a smaller difference that was detected in a recent trial using this metric.⁴⁸ This sample size would also provide ample power the for the absolute eosinophil count and EREFS secondary outcomes.

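### The failure/success sensitivity analysis moves both arms the same way, misses the arm-specific worst case and is undefined for the continuous primary; LOCF does not exclude scores taken after rescue

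*Combined protocol and SAP*

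**What the plan says.** The primary outcome is change in EEsAI from baseline to month 3, compared by analysis of covariance (section 9.4.2). The analysis set is limited to treated participants who have month-3 EEsAI and endoscopy data (9.3), and 9.4.1 confirms that those without outcome data are left out of the primary analyses.

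Two sensitivity analyses are planned:

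- Section 9.4.1: "initially assigning participants lost to follow up to treatment failure, then assigning them to treatment success and comparing the results". It gives no split by arm, no EEsAI value for either label and no list of the outcomes covered.
- Section 9.3: "the last available EEsAI value will be carried forward for any participants who terminate the study or are lost to follow-up". It gives no exception for scores obtained after rescue.

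On rescue during the treatment period, section 6.5.1 says that "the participant would be considered a treatment failure and would exit the study". Such a participant should come back for an early termination visit where that can be done safely, and EEsAI is on the list for that visit (8.4, Visit months 3, 6 and early termination). Section 6.5.1 also asks that rescue wait, where possible, until the month-3 or month-6 assessment, and requires its date and time to be recorded.

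**The concern.** Participants who need rescue before month 3 can leave the primary analysis because they did badly, so the plan's protection against informative dropout lies in these two analyses. Three features weaken it.

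1. Setting every missing participant to failure, then every one to success, moves both arms in the same direction each time. The damaging case is the opposite one, where missing participants on active drug did badly and those on placebo did well. The planned pair does not look there.
2. Failure and success are binary. Without an assigned EEsAI value the analysis cannot be run on a change score. Its wording also leaves out rescue exits and other withdrawals, who are not lost to follow-up in the sense of section 7.2.
3. LOCF is then the only usable sensitivity analysis for the primary. Because it takes the last score of any kind, an early termination EEsAI measured after rescue can enter as an improvement for a participant whom 6.5.1 classes as a failure.

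At stake is whether a reader of the results can judge how much differential dropout they would withstand.

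**Working it through.** **Inputs from the plan.** Section 9.4.1: "For inferential tests, a p value < 0.05 will be considered significant and all tests will be two tailed". Section 9.2: "with a sample size of 30 patients in each group", "a difference in the mean change in EEsAI score of as little of 17", "with a power of 0.9 at an α of 0.05", SD 20. Section 9.2 also says: "Assuming a 20% dropout rate, we plan to randomize 36 patients in each group".

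**The plan's own figure.** n = 2 × 20² × (1.960 + 1.282)² / 17² = 29.1, rounded up to 30 per arm, as stated. 30 × 1.2 = 36. The missing count per arm is therefore 36 − 30 = 6, or 20% × 36 = 7.2, about 7. Both are used below. Responder counts are assumptions, since the plan gives none for this trial.

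**Algebra for a responder outcome.** Let n be randomised per arm, r observed responders and m missing, with subscripts M (mepolizumab) and P (placebo).

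- All failure: (rM − rP)/n
- All success: (rM + mM − rP − mP)/n
- Gap, all success minus all failure: (mM − mP)/n, which is zero when mM = mP
- Worst case (active fail, placebo succeed): (rM − rP − mP)/n. This lies mP/n below the all-failure run and mM/n below the all-success run, so neither run reaches it when both arms have missing participants.

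**Numbers** (n = 36, uncorrected chi-square; differences in percentage points):

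| Assumed case | Complete case | All failure | All success | Worst | Best |
|---|---|---|---|---|---|
| 7 and 7 missing; 17 vs 9 responders | 27.6 (p = 0.035) | 17/36 − 9/36 = 22.2 (p = 0.0497) | 24/36 − 16/36 = 22.2 (p = 0.058) | 17/36 − 16/36 = 2.8 (p = 0.81) | 24/36 − 9/36 = 41.7 (p = 0.0004) |
| 6 and 6 missing; 14 vs 2 remissions | 40.0 (p = 0.0005) | 14/36 − 2/36 = 33.3 (p = 0.0007) | 20/36 − 8/36 = 33.3 (p = 0.004) | 14/36 − 8/36 = 16.7 (p = 0.12) | 20/36 − 2/36 = 50.0 (p < 0.001) |
| 3 and 9 missing; 15 vs 2 remissions | 38.0 (p = 0.001) | 15/36 − 2/36 = 36.1 (p = 0.0003) | 18/36 − 11/36 = 19.4 (p = 0.093) | 15/36 − 11/36 = 11.1 (p = 0.33) | 18/36 − 2/36 = 44.4 (p < 0.001) |

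The 2/30 in the second row follows the 7% placebo remission of a budesonide trial cited in 9.4.2.

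**Continuous primary at the design effect (improvements of 32 and 15).** Suppose values were attached to the labels. With 6 missing per arm, any common value gives 17 × 30/36 = 14.2 points, whatever the value. If missing mepolizumab participants had no change and missing placebo participants improved by 32, the means are 30 × 32/36 = 26.7 and (30 × 15 + 6 × 32)/36 = 17.8. The difference is 8.8, with lower 95% limit 8.8 − 1.994 × 20 × √(2/36) = 8.8 − 9.4 = −0.6.

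**Tipping point.** Put missing participants at their own arm mean, then make those on mepolizumab worse by δ. Significance is lost when the observed difference − 6δ/36 falls to 9.4, so δ = (observed − 9.4) × 6. That is about 46 points for an observed difference of 17, 22 for 13 and 10 for 11. This holds the SD at 20 and treats filled-in values as data, so it is approximate.

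**LOCF after rescue.** If a post-rescue score is 20 points better than the last score before rescue (an assumption, using the plan's threshold for response), each such participant moves that arm's mean by 20/36 = 0.56 points. Six in one arm would move it by 3.3.

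**The case against.** The strongest defence is that the planned analyses are not empty. In the first row the effect shrinks from 27.6 to 22.2 points and the p-value moves from 0.035 to 0.0497 and 0.058, across the plan's threshold. With unequal dropout, often the most worrying pattern, the two runs separate: in the third row they are 36.1 and 19.4 points, and significance is lost. A reader might infer that the pair always returns one answer, or would report robustness whether or not it exists. The documents do not support that: nothing in them says that missing counts will be equal, and p-values and intervals differ even when they are.

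Section 9.4.1 is also a general statement for all outcomes. Failure and success fit the EEsAI remission and response outcomes and the histologic thresholds, and the continuous EEsAI has LOCF. That is fair, but the text does not state this division, and it leaves LOCF alone on the primary.

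The rescue route is conditional. It needs rescue before month 3, no month-3 EEsAI, and an early termination visit late enough after rescue for a 7-day recall to reflect it. Section 6.5.1 asks for rescue to be delayed where possible. In other cases LOCF carries a score from before rescue. The documents give no rescue rate, so the size cannot be fixed. Nor need the error favour the drug: if more placebo participants are rescued, it understates the effect.

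Finally, the worst and best cases are logical limits, not likely results. All of this narrows the point. It does not supply the missing worst case or a rule for post-rescue scores.

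**Conclusion.** The point holds in a limited form. Same-direction assignment gives one risk difference twice when missing counts are equal, gives two that differ by (mM − mP)/n otherwise, and stops short of the arm-specific worst case whenever both arms have missing participants. In the second illustration both planned runs are clearly significant while the worst case, 16.7 points (95% CI −4.3 to 37.6), is not. The analysis cannot be run on the change score as written, and it names only part of the missing group. LOCF has no rule for scores after rescue.

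Two stronger readings should be resisted. One is that neither analysis tests anything: the binary pair does stress the responder outcomes, and LOCF is a defined, if weak, analysis of the primary. The other is that 2.8 to 41.7 points is the true range: it is the span of the extremes under assumed counts.

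The algebra needs only equal numbers randomised per arm. The percentages rest on the assumed responders and on 6 or 7 missing per arm; section 7.1 allows withdrawn participants to be replaced, so the real counts may be higher. This is a recommended improvement and does not invalidate the primary analysis.

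**What to change.** - **Responder outcomes.** Apply the analysis to everyone without month-3 data, not only those lost to follow-up. Keep the two planned runs and add assignment in opposite directions by arm, or a tipping-point grid over the number of successes among the missing in each arm. Say which outcomes it covers.
- **Primary outcome.** Add a delta-adjusted tipping-point analysis of EEsAI change that uses the monthly scores to fill in missing month-3 values. A repeated-measures model is optional: it assumes data missing at random, so it does not itself test informative dropout.
- **Scores after rescue.** State that LOCF does not carry forward an EEsAI dated after rescue, and that these participants count as non-responders in responder outcomes, in line with their classification in 6.5.1. The recorded date and time of rescue make this workable.

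The cost is SAP wording and a few extra tables, with no new data. The sponsor should expect that some sensitivity results may look less favourable than those now planned.
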